#### **10.1.2.2 After flare**

Exposure to study medication in Part B after flare and escape to full-dose CZP will be evaluated by summarizing the total number of CZP or PBO injections, the total number of CZP injections, the total amount of CZP received in mg, the total drug exposure duration in days, the patient time at risk and the total patient years at risk. Summaries will be based on the ETS and presented by treatment group.

Duration of exposure to study medication in Part B after escape to full-dose CZP will be calculated (in days) as:

- The date of the last escape full-dose CZP injection – date of first escape full-dose CZP injection + 14 days for all subjects

If final contact or death occurs prior to the completion of the 14-day period, the exposure duration will be censored at the date of the earliest event.

Patient time at risk in Part B after escape to full-dose CZP will be calculated (in days) as:

- The date of the last escape full-dose CZP injection – date of first escape full-dose CZP injection + 70 days for all subjects

If final contact or death occurs prior to the completion of the 70-day period, the patient time at risk will be censored at the date of the earliest event.

Total patient years at risk will be calculated as the sum of all the relevant patient time at risk (in days) divided by 365.25.

#### **10.1.2.3 Full-dose CZP in Part B**

Exposure to full-dose CZP in Part B will be evaluated by summarizing the total number of CZP injections, the total amount of CZP received in mg, the total drug exposure duration in days, the patient time at risk and the total patient years at risk. Summaries will be based on the FDS. These summaries will be produced presenting a single column “CZP full-dose in Part B (CZP 200mg Q2W)”.

Duration of exposure to full-dose CZP in Part B as double-blind or as escape treatment will be calculated (in days) as:

- The date of the last escape full-dose CZP injection – date of the first escape full-dose CZP injection + 14 days for subjects in the 200mg CZP Q4W and PBO groups who escape to full-dose CZP therapy
- The date of the last escape full-dose CZP injection – date of Week 48 injection + 14 days for subjects in the 200mg CZP Q2W group experiencing a flare
- The date of the last Part B injection – date of Week 48 injection + 14 days for subjects in the 200mg CZP Q2W group who did not flare

If final contact or death occurs prior to the completion of the 14-day period, the exposure duration will be censored at the date of the earliest event.

Patient time at risk in Part B under full-dose CZP therapy will be calculated (in days) as:

- The date of the last escape full-dose CZP injection – date of the first escape full-dose CZP injection + 70 days for subjects in the 200mg CZP Q4W and PBO groups who escape to full-dose CZP therapy
- The date of the last escape full-dose CZP injection – date of Week 48 injection + 70 days for subjects in the 200mg CZP Q2W group experiencing a flare
- The date of the last Part B injection – date of Week 48 injection + 70 days for subjects in the 200mg CZP Q2W group who did not flare

If final contact or death occurs prior to the completion of the 70-day period, the patient time at risk will be censored at the date of the earliest event.

Total patient years at risk will be calculated as the sum of all the relevant patient time at risk (in days) divided by 365.25.

### **10.1.3 Part A and Part B full-dose CZP therapy**

Exposure to full-dose CZP therapy in Part A and/or Part B will be evaluated by summarizing the total number of CZP injections, the total amount of CZP received in mg, the total drug exposure duration in days, the patient time at risk and the total patient years at risk. Summaries will be based on the SS. These summaries will be produced presenting a single column “CZP full-dose in Part A and/or Part B (CZP 200mg Q2W)”.

Duration of exposure to full-dose CZP therapy in Part A and/or Part B will be calculated (in days) as:

- The date of the last Part A full-dose CZP injection – date of first Part A full-dose CZP injection + 14 days for subjects not randomized into Part B. Duration of exposure will be censored at the date of earliest of the following events if any of these events occur prior to the completion of the 14-day period: final contact or death.
- The date of the last Part A full-dose CZP injection – date of first Part A full-dose CZP injection + 14 days for subjects randomized into Part B to the PBO or CZP 200mg Q4W arms who do not experience a flare and do not escape to CZP full-dose therapy. Duration of exposure will be censored at the date of earliest of the following events if any of these events

occur prior to the completion of the 14-day period (first study medication administration in Part B, final contact or death).

- The sum of (date of the last Part A full-dose CZP injection – date of first Part A full-dose CZP injection + 14 days) [1] and (date of the last escape full-dose CZP injection – date of first escape full-dose CZP injection + 14 days) [2] for subjects randomized into Part B to the PBO or CZP 200mg Q4W arms who do experience a flare and do escape to CZP full-dose therapy. If first study medication administration in Part B occurs prior to the completion of the 14 day period for [1], [1] will be censored at the date of this event. If final contact or death occurs prior to the completion of the 14-day period for [2], [2] will be censored at the date of the earliest event.
- The date of the last Part B injection – date of first Part A full-dose CZP injection + 14 days for subjects randomized into Part B to CZP 200mg Q2W arm. If final contact or death occurs prior to the completion of the 14-day period, the exposure will be censored at the date of the earliest event.

Patient time at risk in Part A and or Part B under full-dose CZP therapy will be calculated (in days) as:

- The date of the last Part A full-dose CZP injection – date of first Part A full-dose CZP injection + 70 days for subjects not randomized into Part B. Patient time at risk will be censored at the date of earliest of the following events if any of these events occur prior to the completion of the 70-day period: final contact or death.
- The date of the last Part A full-dose CZP injection – date of first Part A full-dose CZP injection + 70 days for subjects randomized into Part B to the PBO or CZP 200mg Q4W arms who do not experience a flare and do not escape to CZP full-dose therapy. Patient time at risk will be censored at the date of earliest of the following events if any of these events occur prior to the completion of the 70-day period (first study medication administration in Part B, final contact or death).
- The sum of (date of the last Part A full-dose CZP injection – date of first Part A full-dose CZP injection + 70 days) [1] and (date of the last escape full-dose CZP injection – date of first escape full-dose CZP injection + 70 days) [2] for subjects randomized into Part B to the PBO or CZP 200mg Q4W arms who do experience a flare and do escape to CZP full-dose therapy. If first study medication administration in Part B occurs prior to the completion of the 70-day period for [1], [1] will be censored at the date of this event. If final contact or death occurs prior to the completion of the 70-day period for [2], [2] will be censored at the date of the earliest event.
- The date of the last Part B injection – date of first Part A full-dose CZP injection + 70 days for subjects randomized into Part B to CZP 200mg Q2W arm. If final contact or death occurs prior to the completion of the 70-day period, the patient time at risk will be censored at the date of the earliest event.

Total patient years at risk will be calculated as the sum of all the relevant patient time at risk (in days) divided by 365.25.

Exposure data will be listed.

## 10.2 Adverse events

### Pre-Treatment and Post-Treatment AEs

Adverse events with start date prior to first administration of study medication will be defined as pre-treatment AEs. No tabular summaries of these events will be produced although they will be included in listings.

Adverse events that start more than 70 days after the last administration of study medication will be defined as post-treatment AEs. No tabular summaries of these events will be produced although they will be included in listings.

### Treatment-Emergent AEs (TEAEs)

Treatment emergent AEs (TEAEs) will be defined and summarized in four different ways:

[1] TEAEs in Part A: will be defined as all AEs starting on or after the date of first study medication in Part A and up to 70 days after the last dose of study medication in Part A and before the date of the first study medication in Part B if any.

[2] TEAEs in Part B prior to flare: will be defined as all AEs starting on or after the date of first study medication in Part B and up to 70 days after the last dose of study medication in Part B. AEs occurring more than 70 days after the last dose in Part B will not be considered treatment emergent, regardless of whether this occurs during the SFU period, or after a treatment gap of more than 70 days. AEs which emerge post-flare will be excluded from any summary tables of TEAEs in Part B prior to flare.

[3] TEAEs in Part B in subjects experiencing a flare: Pre-flare TEAEs in Part B will be defined as any TEAEs in Part B with an onset date before the start date of escape therapy. Post-flare TEAEs in Part B will be defined as any TEAEs in Part B with an onset date on or after the start date of escape therapy.

[4] TEAEs in Part B under CZP full-dose therapy: These will be defined for subjects in the FDS who ever received a dose of CZP 200mg Q2W during Part B as double-blind or as escape treatment.

TEAEs in Part B under CZP full-dose therapy will be defined as follows:

- In subjects randomized into Part B to the PBO or CZP 200mg Q4W arm who do experience a flare and do escape to CZP full-dose therapy, TEAEs under CZP full-dose therapy will include all post-flare TEAEs in Part B
- In subjects randomized into Part B to CZP 200mg Q2W arm, TEAEs under CZP full-dose therapy will include all TEAEs in Part B

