### **2.4       Determination of sample size**

It is anticipated that approximately 210 subjects will be randomized in a 1:1:1 ratio to the CZP 200mg Q2W, CZP 200mg Q4W, and PBO treatment groups. The primary efficacy analysis is based on the proportion of subjects who do not experience a flare during Part B of the study. The proportion of subjects who do not experience a flare during Part B is assumed to be 80%, 75%, and 45% for the CZP 200mg Q2W, CZP 200mg Q4W, and PBO treatment groups, respectively. Given these assumptions, a sample size of 70 subjects per group provides 98% power to detect a significant difference between the CZP 200mg Q2W dose and PBO and 94% power to detect a significant difference between the CZP 200mg Q4W dose and PBO using a 2-sided significance level of 0.05.

Given that subjects enter Part B only if they have achieved sustained remission in Part A, it is necessary to estimate the number of subjects needed to enroll in Part A. It is assumed that approximately 28% of subjects enrolled in Part A will achieve sustained remission and qualify for Part B. This means that about 750 subjects will be enrolled in Part A in order to have 210 subjects who are randomized into Part B.

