## **AE Summaries**

All AE summary tables described in this Section will be produced four ways, ie for each of the following types of AEs:

- a. TEAEs in Part A, based on the SS
- b. TEAEs in Part B prior to flare, based on the SSB
- c. TEAEs in Part B for subjects experiencing a flare, based on the ETS
- d. TEAEs in Part B under CZP full-dose therapy, based on the FD

SAEs will be classified by SOC, High Level Term (HLT), and PT according to MedDRA®. The latest version available to the sponsor at the time of coding will be used. Summary tables will display the number and percentage of subjects experiencing the TEAEs and number of TEAEs. In this style of output, “number of TEAEs” will include all occurrences of a TEAE including repeat occurrences in individual subjects, while “number of subjects” will count each subject only once.

Overall summaries of AEs will be produced to present the number of events and number and percentage of subjects with:

- Any TEAE
- Any serious TEAE
- Any TEAE leading to study discontinuation
- Permanent withdrawal of study medication due to TEAEs
- Any drug-related TEAE
- Any severe TEAE
- All Deaths (AEs leading to death)
- Deaths (TEAE leading to death)

In addition, the following AE summaries will be presented:

- All TEAEs by primary SOC, HLT, and PT (for the Parts/Analysis sets a, b, c, d)
- All serious TEAEs by primary SOC, HLT, and PT (for the Parts/Analysis sets a, b, c, d)
- All TEAEs leading to permanent discontinuation of study drug by primary SOC, HLT, and PT (for the Parts/Analysis sets a, b, c, d)
- All TEAEs leading to death by primary SOC, HLT, and PT (for the Parts/Analysis sets a, b, c)
- All TEAEs by primary SOC, PT, and maximum intensity (for the Parts/Analysis sets a, b, c, d)
- All TEAEs by primary SOC, PT, and maximum relationship (for the Parts/Analysis sets a, b, c, d)

- All serious TEAEs by primary SOC, PT and maximum relationship (for the Parts/Analysis sets a, b, c, d)
- All TEAEs above reporting threshold of 5% by primary SOC and PT (for the Parts/Analysis sets a, b, c, d)
- All non-serious TEAEs above reporting threshold of 5% by primary SOC and PT (for the Parts/Analysis sets a, b, c)
- All injection related TEAEs by primary SOC, HLT, and PT (for the Parts/Analysis sets a, b, c, d)

AE summary tables will also be produced to display the exposure adjusted incidence rate (EAIR) with associated 95% CI, and the exposure adjusted event rate (EAER):

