**Table 10.2: Definitions of Markedly Abnormal Biochemistry Values**

Parameter (SI units)	Markedly Abnormal Definition	
	Low	High
AP	N/A a	>3 x ULN
ALT	N/A	>3 x ULN
AST	N/A	>3 x ULN
Calcium (mmol/L)	<1.75	>3.125
CPK	N/A	>4 x ULN
Creatinine	N/A	>1.8 x ULN
Glucose (mmol/L)	<2.22	>13.89
Potassium (mmol/L)	<3.0	>6.4
Sodium (mmol/L)	<125	N/A
Total bilirubin	N/A	≥2 x ULN
Uric acid	N/A	≥3 x ULN

a N/A=not applicable, ALT=alanine aminotransferase, AP=alkaline phosphatase, AST=aspartate aminotransferase, CPK=creatinine phosphokinase.

The number and percentage of subjects with markedly abnormal hematology or biochemistry values will be summarized by visit and for any visit (excluding the SFU visit) separately for each treatment period. Subject numbers for subjects with any markedly abnormal hematology or biochemistry value will be tabulated.

Summaries for Part A will be presented by axSpA subpopulation and overall in the SS. Summaries for Part B will be presented by treatment group in the SSB excluding any post-flare assessments in the subset of subjects experiencing a flare in Part B and start escape therapy. For the subset of subjects experiencing a flare in Part B and start escape therapy, separate summaries will be produced using the ETS and will present only the post-flare assessments by treatment group.

For the derivation of the number and percentage of subjects with markedly abnormal hematology or biochemistry at any visit within a treatment period, only post-baseline assessments within the corresponding treatment period will be considered (excluding the SFU visit). In Part B, derivations will be done excluding all assessments performed after the start of escape therapy in subjects experiencing a flare in Part B and start escape therapy. In the subset of subjects experiencing a flare in Part B and start escape therapy, derivations will be done including only the assessments performed after the start of escape therapy.

A by-subject listing of markedly abnormal values will be provided separately.

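### Part B adverse-event tables by arm are cut at escape, so placebo is observed for less time, and the discontinuation, severity, relatedness and injection-related tables carry no exposure adjustment

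*SAP*

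**What the plan says.** SAP section 10.2 defines TEAEs in Part B prior to flare as events from the first Part B dose up to 70 days after the last Part B dose, and adds that "AEs which emerge post-flare will be excluded from any summary tables of TEAEs in Part B prior to flare". The next definition in that section places post-flare events on or after the start date of escape therapy. Section 10.1.2.1 censors time at risk at the start of escape full-dose CZP, so numerator and denominator match.

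The default content under AE Summaries is crude: "Summary tables will display the number and percentage of subjects experiencing the TEAEs and number of TEAEs". Exposure-adjusted incidence and event rates (EAIR, EAER) are then specified for all TEAEs and all serious TEAEs, for every table set including set b. The end of section 10.2 adds both rates to the tables for AEs of interest, hepatic events, and hypersensitivity and anaphylactic reactions.

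These set b outputs have no time denominator:
- the overall-summary rows for TEAEs leading to discontinuation or withdrawal of study medication, drug-related TEAEs and severe TEAEs
- the tables for TEAEs leading to discontinuation, by maximum intensity, by maximum relationship (all and serious), and for injection-related TEAEs
- the table of TEAEs leading to death, although fatal events are serious and so also fall in the serious-TEAE table that has rates
- the two 5% threshold tables.

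Section 10.3 handles laboratory abnormalities the same way: "The number and percentage of subjects with markedly abnormal hematology or biochemistry values will be summarized by visit and for any visit". It excludes the follow-up visit and, for Part B, assessments after the start of escape.

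**The concern.** How long a subject contributes to set b depends on whether that subject escapes, and escape follows from the primary endpoint. Section 2.4 gives flare-free proportions "assumed to be 80%, 75%, and 45% for the CZP 200mg Q2W, CZP 200mg Q4W, and PBO treatment groups, respectively". A trial that succeeds on its primary endpoint will therefore observe placebo subjects for less time in these tables. A percentage of subjects with an event rises with observation time, so equal event rates produce unequal percentages, lower on placebo.

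Safety and tolerability of CZP is a secondary objective. Discontinuations, severe events and related events are the usual basis for tolerability statements, and they bear on the choice between continuing and withdrawing treatment.

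The SAP already deals with the same problem elsewhere. For uveitis, IBD and psoriasis events it plans counts and percentages in Part A (8.3.1.17). In Part B, where events are cut at Escape Week 0, it adds incidence and event rates (8.3.2.9).

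**Working it through.** **Check that the flare rates are those used for sizing.** Section 2.4 states that "a sample size of 70 subjects per group provides 98% power to detect a significant difference between the CZP 200mg Q2W dose and PBO". For Q4W it gives 94%. For 80% vs 45% and 75% vs 45% with 70 per arm, two-sided 0.05:
- normal approximation, pooled variance under the null: 99.4% and 96.0%
- with continuity correction: 98.9% and 94.1%
- Fisher exact: 98.9% and 94.0%.

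The stated figures are reproduced to within about 2 points, so flare proportions of 20%, 25% and 55% are the plan's own.

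**Length of observation.** The last Part B dose is at Week 94, which is Part B week 46 (section 2.3.4). A subject who does not escape counts to 46 + 10 = 56 weeks. A subject who escapes counts to flare + 2 weeks, the usual delay in section 2.3.3. Flare timing is not in the SAP and is assumed.

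Mean time at risk = P(no flare) × 56 + P(flare) × (mean flare week + 2).

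Flares uniform over weeks 4–48 (mean 26, window 28):
- Q2W: 0.80 × 56 + 0.20 × 28 = 50.4
- Q4W: 0.75 × 56 + 0.25 × 28 = 49.0
- PBO: 0.45 × 56 + 0.55 × 28 = 40.6, which is 1 − 40.6/50.4 = 19% below Q2W.

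Flares early, uniform over weeks 4–24 (mean 14, window 16):
- Q2W: 0.80 × 56 + 0.20 × 16 = 48.0
- PBO: 0.45 × 56 + 0.55 × 16 = 34.0, which is 29% below Q2W.

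| Assumed flare timing | Q2W (weeks) | PBO (weeks) | PBO shorter by |
|---|---|---|---|
| Uniform, weeks 4–48 | 50.4 | 40.6 | 19% |
| Exponential, weeks 4–48 | 50.2 | 39.0 | 22% |
| Uniform, weeks 0–48 | 50.0 | 39.5 | 21% |
| Constant hazard from week 0 | 49.8 | 37.8 | 24% |
| Uniform, weeks 4–24 | 48.0 | 34.0 | 29% |

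**Crude percentage at one true rate in all arms.** Expected percentage = mean of 1 − exp(−rate × weeks/52.18). The event rate is also an assumption. With flares over weeks 4–48 (uniform or exponential):

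| True rate per patient-year | Q2W | PBO | Gap (points) |
|---|---|---|---|
| 0.1 | 9.1–9.2% | 7.1–7.4% | about 2 |
| 0.2 | 17.5% | 13.7–14.2% | 3–4 |
| 0.5 | 37.8% | 30.1–31.3% | 6–8 |

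With the early-flare pattern the same formula gives 8.7% vs 6.2% at 0.1 and 36.0% vs 26.4% at 0.5. Crude event counts scale directly with the time at risk. With time at risk censored at escape, EAIR has the same expectation in every arm.

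**Laboratory window.** Section 10.3 excludes the follow-up visit, so a subject who does not escape counts to about week 48, not 56. Flares uniform over weeks 4–48 give Q2W 0.80 × 48 + 0.20 × 28 = 44.0 and PBO 0.45 × 48 + 0.55 × 28 = 37.0, 16% shorter. The exponential version gives 19%.

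**The case against.** The strongest reply is that the main tables are already protected. All TEAEs and all serious TEAEs have EAIR and EAER by preferred term, and so do the tabulated AEs of interest, hepatic events and hypersensitivity. Every term in the 5% threshold tables also appears, with its rate, in the all-TEAE table. Section 10.1.2.1 tabulates patient-years by arm. All of this stands, and it limits the point to the rows and tables listed above.

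Three stronger readings are tempting, and the SAP does not support them:
- **Adverse-event follow-up ends at escape.** It does not. Later events are collected and summarised in sets c and d. Only the set b table is cut, which keeps events on escape CZP from being attributed to placebo. Sets c and d do not, however, give a randomised comparison over equal follow-up.
- **Most Part B harm tables are crude only.** Once the AE-of-interest tables are counted, adjusted and crude-only AE tables are about equal in number.
- **The 56-week window and the derived time at risk also fit the laboratory tables.** They do not. The derived time includes a 70-day tail in which no laboratory assessment counts. Most of that tail falls on CZP, so using it would tilt the rates slightly in favour of CZP.

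It can also be said that the gaps are small for this trial. With 70 per arm, the standard errors of the differences at 0.1, 0.2 and 0.5 per patient-year are about 4.6, 6.1 and 8.0 points, so each gap in the table of crude percentages lies within one standard error. The tables are descriptive, and the distortion runs against CZP, so it hides no harm of CZP. These arguments lower the priority. They do not remove a distortion whose direction follows from the design.

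**Conclusion.** The point holds in limited form. In set b, the overall-summary rows for discontinuation, drug-related and severe TEAEs, and the tables for discontinuation, maximum intensity, maximum relationship and injection-related TEAEs, compare arms over unequal follow-up without adjustment. Placebo time at risk is about 19–29% below Q2W. At equal true rates CZP looks modestly worse: about 2 points at 0.1 per patient-year and 6–8 points at 0.5 with flares spread over weeks 4–48, and somewhat more if flares cluster early.

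The size rests on the SAP's planned flare proportions and on assumed flare timing and event rates. The planned proportions count withdrawals as flares (section 3.2.22), and those subjects need not escape. If 20% of flares are withdrawals without escape, the PBO-to-Q2W ratio of mean time is 0.79–0.81, against 0.78–0.81 without that allowance. The direction does not depend on these choices as long as escape is more frequent on placebo. Priority is minor to moderate.

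**What to change.** For set b:
- Add EAIR with the 95% CI already defined in section 10.2 (time at risk censored at escape), and patient-years per arm, to the overall-summary rows for discontinuation, drug-related and severe TEAEs, and to the tables for TEAEs leading to discontinuation, maximum intensity, maximum relationship and injection-related TEAEs.
- State that between-arm statements on Part B adverse events rest on EAIR, not on crude percentages.
- Footnote the 5% threshold tables to the all-TEAE table with EAIR. They need no new columns.
- For any-visit markedly abnormal laboratory values, footnote the unequal follow-up and rely on the by-visit summaries already planned. Alternatively, use a denominator that ends at the last counted laboratory assessment, without the 70-day tail.

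For injection-related TEAEs, a footnote should say that the time at risk includes a tail after the last dose in which no injections are given.

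The cost is SAP wording and slightly wider tables. For the AE tables the time at risk is already derived, and no new data are needed. Only the optional laboratory denominator would require a new derivation.
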